## Clinical Investigation Plan

[REDACTED]

[REDACTED]

### 4.1.2 Primary Effectiveness Endpoint

The primary effectiveness endpoint for this clinical trial is freedom from documented (symptomatic or asymptomatic) AF/AFL/AT episodes of >30 seconds duration that are documented by 12-lead ECG, transtelephonic monitoring (TTM) or Holter monitor after the initial catheter ablation procedure through 12-months of follow-up (9 months after a 90-day blanking period).

AF/AFL/AT recurrence during the 90-day blanking period ( $\leq 90$  days post-initial procedure) will not be considered a treatment failure. One repeat procedure will be allowed for ablation of AF/AFL/AT

[REDACTED]

[REDACTED]

[REDACTED]

## Clinical Investigation Plan

recurrence 31-80 days after the initial procedure and will not be considered a treatment failure. Failure to achieve acute procedural success (confirmation of entrance block after a 20-minute minimum waiting period) during the last ablation procedure with the TactiFlex SE catheter will constitute failure to achieve this endpoint. After the 90-day blanking period, use of Class I or III AADs will not count as a therapy failure provided that only previously failed Class I or III AADs are taken at doses that do not exceed the previously failed dose.

AF/AFL/AT recurrence will only be assessed by 12-lead ECG, TTM, and Holter monitoring devices for assessment of this primary endpoint so that all subjects are monitored equally with devices of the same sensitivity and specificity (recurrence data collected from other devices such as pacemakers, ICDs, or ICMs will not be included in the assessment). ECG, TTM, and Holter data collected from sites will be evaluated by a core laboratory to ensure independent and unbiased assessment of AF/AFL/AT recurrence for endpoint analysis.

There are multiple situations in which subjects will be considered primary effectiveness endpoint failures:

- If the subject fails to achieve acute procedural success, defined as confirmation of entrance block in all pulmonary veins after a minimum waiting period of 20-minutes, during last ablation procedure performed with the TactiFlex SE catheter, or
- If documented AF/AFL/AT recurrence (>30 second episode) occurs at any time after the blanking period (>90 days after the initial procedure), or
- If the subject requires a repeat procedure for the treatment of AF >80 days after the initial procedure, the subject will be considered an effectiveness endpoint failure regardless of documentation of a >30 second AF/AFL/AT episode, or
- If the subject requires a second repeat AF ablation procedure ≤80 days after the initial procedure, or
- Any use of a new class I or III AAD for AF after the blanking period, or
- Any use of a class I or III ADD for AF at a dose higher than that previously failed by the patient, or
- If the subject requires a cardioversion (electrical or pharmacological) for the treatment of AF after the blanking period, or
- If the subject has a continuous atrial arrhythmia throughout a 12-lead ECG recording after the blanking period indicating AF/AFL/AT recurrence, this will be considered sufficient documentation of recurrence unless there is evidence that the recorded arrhythmia is short-lived and less than 30 seconds as determined by the investigator, or
- Any ablation in the left atrium using an ablation catheter other than TactiFlex SE.

Cavotricuspid isthmus (CTI)-dependent AFL that occurs alone either during or after the blanking period will be considered an exception to being considered a recurrence, as CTI-dependent AFL is easily treated with cavotricuspid isthmus ablation and is not an iatrogenic arrhythmia following a left atrial ablation procedure for AF. Occurrence of CTI-dependent AFL confirmed by entrainment maneuvers that occurs at any time during the follow-up period and is ablated, will not be considered a primary effectiveness endpoint failure.

The performance goal (PG) is set at 50% based on the chronic acceptable success rate for paroxysmal AF at 12-months in the 2017 Consensus Statement [17]. The 50% chronic acceptable success rate

---

 For subjects that have a repeat ablation procedure ≤80 days after the initial procedure, only failure to achieve acute procedural success during the repeat procedure will contribute to primary effectiveness endpoint.

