### 3.1 Clinical Investigation Procedures and Follow-up Schedule

The visit schedule for subjects is shown in **Figure 5**. Once eligibility is confirmed, the subject will undergo a study ablation procedure for treatment of their PAF condition. A blanking period of 90-days will be employed after the initial ablation procedure, followed by a 9-month evaluation period. The total follow-up period will be for 12 months. Medication adjustments, cardioversions, and one repeat ablation procedure may be performed in the blanking period without being considered a primary effectiveness endpoint failure (repeat ablation for AF must be performed 31-80 days after the initial procedure). Subjects must be off Class I and III antiarrhythmic drugs (AADs) after the blanking period, unless clinically justified. Follow-up assessments will occur either in-person at the clinic or via phone contact after the procedure. The scheduled follow-up visits will occur before the patient leaves the hospital and then at 7-days (phone call), 5-weeks (phone call), 3-months (in-person visit), 6-months (phone call), and 12-months (in-person visit) after the initial procedure. The subject will be exited from the trial after completing their 12-month follow-up visit.

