### 4.1.2.1 Rationale for Selection of the Primary Effectiveness Endpoint

The guideline published by the 2017 Consensus Statement [17] was referred to when defining the primary effectiveness end-point for this clinical investigation. The following criteria were defined from this document for use in this clinical investigation: the definition of detectable AF defined as AF/AFL/AT of at least 30 seconds duration when assessed with ECG monitoring; an acceptable chronic success rate of 50% for PAF.

Counting the use of new or higher than previously failed doses of AADs after the blanking period as effectiveness failures is consistent with the primary effectiveness endpoint recommendations in the FDA Guidance on Clinical Study Designs for Percutaneous Catheter Ablation for the Treatment of Atrial Fibrillation [32].

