Subjects using Class I or III AADs without documented AF/AFL/AT recurrence during the follow-up period will not be considered primary effectiveness endpoint failures. However, if the subject requires a new Class I or III AAD or a previously failed Class I or III AAD at a dose greater than the highest ineffective historical dose for AF after the therapy blanking period ( $\geq 91$  days post-procedure), they will be considered a primary effectiveness endpoint failure.

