### 6.5 Blanking Period

A blanking period of 90-days will be employed after the initial ablation procedure and then followed by a 9-month evaluation period for a total of 12-months of follow-up. Early recurrence of AF, AFL, or AT within the blanking period will not be considered treatment failures. During the blanking period, adjustment of antiarrhythmic medications, cardioversions, and one repeat ablation procedure (31-80 days after the initial procedure) may be performed.

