## Clinical Investigation Plan

The following assessments need to be performed if a repeat ablation is required.

- Neurological assessment and administration of the NIHSS by a certified assessor must be performed within 14-days of the repeat ablation procedure.
- Thrombus assessment must be performed as outlined in **Section 6.2.4** prior to ablating the subject.
- Pregnancy test must be performed as per **Section 6.2.3**, if applicable.
- Verification of the exclusion of pericardial effusion by ICE or TTE must also be performed prior to the conclusion of the procedure.
- Document adverse events and protocol deviations

A 7-day ( $\pm 2$  days) follow-up phone call to the subject will need to be conducted after the repeat procedure. All other follow-up visits will occur as previously scheduled from the initial ablation procedure. Note that the 90-day blanking period is still in place from the initial procedure.

If the subject requires a repeat procedure for AF/AFL/AT recurrence  $>80$  days after the initial ablation procedure, or the subject requires a third ablation procedure, then the subject will be considered an effectiveness endpoint failure regardless of documentation of a  $>30$  second AF/AFL/AT episode.

The data from the entire procedure recorded on the investigational EnSite system should be anonymized and labeled with the study information and Subject ID and sent to Abbott within a reasonable time frame (within 10 days).

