1.4.1.2 Primary Effectiveness Endpoint

The primary effectiveness endpoint for this clinical trial is freedom from documented (symptomatic or asymptomatic) AF/AFL/AT episodes of >30 seconds duration that are documented by 12-lead ECG, transtelephonic monitoring (TTM) or Holter monitor after the initial catheter ablation procedure through 12-months of follow-up (9 months after a 90-day blanking period).

AF/AFL/AT recurrence during the 90-day blanking period (≤ 90 days post-initial procedure) will not be considered a treatment failure. One repeat procedure will be allowed for ablation of AF/AFL/AT recurrence 31-80 days after the initial procedure and will not be considered a treatment failure. Failure to achieve acute procedural success (confirmation of entrance block after a 20-minute minimum waiting period) during the last ablation procedure¹ with the TactiFlex SE catheter will constitute failure to achieve this endpoint. After the 90-day blanking period, use of Class I or III AADs will not count as a therapy failure provided that only previously failed Class I or III AADs are taken at doses that do not exceed the previously failed dose.

AF/AFL/AT recurrence will only be assessed by 12-lead ECG, TTM, and Holter monitoring devices for assessment of this primary endpoint so that all subjects are monitored equally with devices of the same sensitivity and specificity (recurrence data collected from other devices such as pacemakers, ICDs, or ICMs will not be included in the assessment). ECG, TTM, and Holter data collected from sites will be evaluated by a core laboratory to ensure independent and unbiased assessment of AF/AFL/AT recurrence for endpoint analysis.

There are multiple situations in which subjects will be considered primary effectiveness endpoint failures:

- If the subject fails to achieve acute procedural success, defined as confirmation of entrance block in all pulmonary veins after a minimum waiting period of 20-minutes, during last ablation procedure performed with the TactiFlex SE catheter, or
- If documented AF/AFL/AT recurrence (>30 second episode) occurs at any time after the blanking period (>90 days after the initial procedure), or
- If the subject requires a repeat procedure for the treatment of AF >80 days after the initial procedure, the subject will be considered an effectiveness endpoint failure regardless of documentation of a >30 second AF/AFL/AT episode, or

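### The primary effectiveness failure list conflicts with other current text on three narrow points: an undated higher-dose AAD rule, a CTI-only third ablation, and who decides on a 12-lead ECG recurrence

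*Protocol*

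**What the plan says.** CIP 4.1.2 lists the situations that make a subject a primary effectiveness failure, and SAP 1.4.1.2 repeats the list. Three entries meet other current text.

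**(a) Higher-dose antiarrhythmic drug.** The bullet reads "Any use of a class I or III ADD for AF at a dose higher than that previously failed by the patient" (ADD evidently means AAD). It carries no time limit, while the new-drug bullet before it and the cardioversion bullet after it are both limited to the time after blanking. Elsewhere:
- CIP 3.1: "Medication adjustments, cardioversions, and one repeat ablation procedure may be performed in the blanking period without being considered a primary effectiveness endpoint failure".
- CIP 4.1.2.1, repeated below the list in SAP 1.4.1.2: "Counting the use of new or higher than previously failed doses of AADs after the blanking period as effectiveness failures".
- CIP 6.2.2 applies the rule to a previously failed drug "at a dose greater than the highest ineffective historical dose for AF after the therapy blanking period", which it puts at day 91 or later.
- CIP 6.5 permits AAD adjustment: "During the blanking period, adjustment of antiarrhythmic medications, cardioversions, and one repeat ablation procedure".
- SAP 1.4.1.2, above the list: "After the 90-day blanking period, use of Class I or III AADs will not count as a therapy failure", on condition that only previously failed drugs are taken, at no more than the failed dose.

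**(b) Third ablation.** CIP 6.6.4 covers late repeat procedures, then adds "or the subject requires a third ablation procedure, then the subject will be considered an effectiveness endpoint failure". CIP 4.1.2 and SAP 1.4.1.2 say that entrainment-confirmed CTI-dependent flutter that "occurs at any time during the follow-up period and is ablated, will not be considered a primary effectiveness endpoint failure".

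**(c) 12-lead ECG.** A continuous arrhythmia on a 12-lead ECG after blanking counts as recurrence unless the investigator determines, on evidence, that it lasted under 30 seconds. CIP 3.2, CIP 4.1.2 and SAP 1.4.1.2 give the evaluation of recurrence to the core laboratory. CIP 6.7 says that the core laboratory's findings are what the effectiveness analysis uses.

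**The concern.** This is a single-arm, unblinded trial tested against a 50% performance goal, so the rate depends entirely on how each subject is classified. A derivation programmed from the list as written would under (a) fail a subject for a dose change during blanking that CIP 3.1 says is not a failure. Under (b) the CIP classifies the same subject in two ways. Under (c) an unblinded investigator holds a decision that can only remove failures from an endpoint described as independently assessed. If these points stay open, they will be settled once outcomes are known.

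The three powered secondary endpoints reuse the primary definition and inherit the problems, with one limit. A subject whose permitted repeat was in the left atrium already fails the single-procedure endpoint, so the third-procedure conflict then reaches only the AAD-free and symptomatic endpoints.

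**Working it through.** **Comparing the texts**

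| Situation | Failure list and exception (CIP 4.1.2, SAP 1.4.1.2) | Other text | Result |
|---|---|---|---|
| Higher dose during blanking, none later | Failure, read literally | Not a failure (CIP 3.1, 4.1.2.1, 6.2.2, 6.5; SAP text around the list) | Conflict; no passage supports the undated reading |
| Initial ablation, permitted repeat on day 50, entrainment-confirmed CTI flutter alone ablated on day 200 | Not a failure | Failure (CIP 6.6.4) | Conflict within the CIP; the visible SAP has only the exception |
| Continuous arrhythmia on a post-blanking 12-lead ECG; investigator judges it under 30 seconds, core laboratory does not | Not a failure by the ECG bullet | Failure if core laboratory findings are used (CIP 6.7) | No visible rule says which prevails |

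A lesser mismatch sits beside (b). The late-repeat bullet speaks of treating AF, where CIP 6.6.4 speaks of AF/AFL/AT recurrence. The bullet's own ending and the allowance of one AF/AFL/AT repeat on days 31-80 point to the wider reading, so this is loose wording. The bullets fail to match 6.6.4 only for a non-CTI right-atrial re-ablation on days 81-90, or later without a qualifying recording. Late left-atrial re-ablation fails anyway: 6.6.4 bars the study catheter from day 81, and the list fails any left-atrial ablation with another catheter.

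**Scale**

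The plan gives no figure to reproduce here; alpha, the test, the assumed rate and the sample-size derivation are redacted. Inputs from the documents are N = 305 in the main study (CIP 5.6) and a goal of 50% (CIP 4.1.2). Assumed: an exact binomial test at one-sided 2.5%, with all 305 analysed.

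- One subject moves the rate by 100/305 = 0.33 points (100/250 = 0.40 if 250 were analysed).
- The smallest r with P(X ≥ r | 305, 0.50) ≤ 0.025 is r = 171: 171/305 = 56.1%, tail probability 0.0195.
- The SAP estimates the rate by Kaplan-Meier. Without censoring, the lower 97.5% bound exceeds 50% from 170 successes (plain Greenwood) or 171 (log-log), so the exact threshold is a fair stand-in.
- At one-sided 5% (assumed) the thresholds are 168 exact, 167 plain and 168 log-log.
- At an assumed 290 or 275 analysed, the exact 2.5% thresholds are 163 (56.2%) and 155 (56.4%).

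If k subjects are reclassified, the verdict can change only when observed successes lie between 171 − k and 170 + k. The upper part of the range, from 171, applies to moves from success to failure; the lower part, up to 170, to moves from failure to success. The k values are illustrations.

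| k | Range of successes | Range of rates |
|---|---|---|
| 1 | 170-171 | 55.7-56.1% |
| 5 | 166-175 | 54.4-57.4% |
| 13 | 158-183 | 51.8-60.0% |

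Power under the same assumptions, if 1% or 3% of subjects moved from success to failure: from 0.927 to 0.864 or 0.652 at an assumed true rate of 60%, and from 0.9995 to 0.998 or 0.985 at 65%.

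**The case against.** The strongest reply is that the visible text largely answers (a) and (b), and that all three are editorial.

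On (a), every other passage dates the rule, the SAP does so immediately above and below its list, and the bullet taken alone would even catch doses before ablation. A literal error would also lower the success rate, against the sponsor's interest. The point about intent stands. The bullet is still the operative wording, and the SAP, which should settle derivation, repeats the omission.

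On (b), 6.6.4 can be read as a third ablation for recurrence, and 4.1.2 says isolated CTI-dependent flutter is not a recurrence. The case is also rare, because CIP 6.3.5 requires CTI ablation at the procedure for subjects with known or induced typical flutter. Rarity is fair. But 6.6.4 uses the third procedure twice as a separate, unqualified condition and does not refer to the exception.

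On (c), the bullet requires evidence, and a short tracing cannot show total duration, so information from the site is a sensible input. That stands, but the bullet gives the investigator the determination and not merely the submission of evidence.

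Two cautions also stand. Redacted text, including parts of CIP 4.1.2, CIP 8.2.1.2, SAP 2.3.1.2 and SAP Appendix E, may hold derivation or precedence rules. And no documentary basis exists for any particular k.

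**Conclusion.** The concern holds. The list is wrong as written on three narrow points: an omission whose intent is clear (a), two answers within the CIP for a CTI-only third ablation (b), and two decision-makers for one ECG recurrence (c).

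The size is about 0.33 points per reclassified subject at N = 305, and the number of such subjects cannot be derived from the documents. Direction is mixed: dating the bullet and applying the CTI exception remove failures, while core laboratory control of the ECG decision and the AF/AFL/AT wording can add some. Few subjects should fall into these situations, so trial success probably does not change unless the observed rate lies close to the threshold, about 56% under the assumed test. The reported primary and secondary rates can change. This deserves correction because it concerns the confirmatory definition, subject to what the redacted text may contain.

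**What to change.** - **(a)** Reconcile the time limit of the higher-dose bullet in CIP 4.1.2 and SAP 1.4.1.2 with the dated text in CIP 4.1.2.1 and 6.2.2 and with the blanking provisions in CIP 3.1 and 6.5.
- **(b)** Reconcile the third-ablation sentence in CIP 6.6.4 with the CTI exception in CIP 4.1.2 by explicit cross-reference. Align the arrhythmia named in the late-repeat bullet with 6.6.4, and carry the agreed text into SAP 1.4.1.2.
- **(c)** In the 12-lead ECG bullet of both documents, replace the investigator's determination with adjudication by the core laboratory, which considers any evidence of short duration that the investigator submits. State in the SAP, as CIP 6.7 does, that core laboratory findings are used for analysis.

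The cost is a few words in each document and no new data. Because the changes move the rate in both directions, they should be agreed before outcome data are reviewed.

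### The failure criterion for a higher-than-failed AAD dose lacks the post-blanking limit and so conflicts with the protocol's own rules on drug adjustment during blanking

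*Protocol*

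**What the plan says.** The failure list in Protocol 4.1.2, copied in SAP 1.4.1.2, contains two drug criteria next to each other. The first is limited in time: "Any use of a new class I or III AAD for AF after the blanking period". The second is not: "Any use of a class I or III ADD for AF at a dose higher than that previously failed by the patient". It also misprints the drug abbreviation, in both documents.

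Other text bears on when a higher dose counts:

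- Protocol 3.1: "Medication adjustments, cardioversions, and one repeat ablation procedure may be performed in the blanking period without being considered a primary effectiveness endpoint failure".
- Protocol 6.5 sets the length, "A blanking period of 90-days will be employed after the initial ablation procedure", and says that during it "adjustment of antiarrhythmic medications, cardioversions, and one repeat ablation procedure (31-80 days after the initial procedure) may be performed".
- Protocol 6.2.2 makes a previously failed drug a failure when it is needed "at a dose greater than the highest ineffective historical dose for AF after the therapy blanking period", and gives the start as day 91 or later.
- Protocol 4.1.2.1 and the end of SAP 1.4.1.2 give the rationale: "Counting the use of new or higher than previously failed doses of AADs after the blanking period as effectiveness failures".
- The narrative ahead of the list, in both documents, begins "After the 90-day blanking period, use of Class I or III AADs will not count as a therapy failure" and adds the proviso that only previously failed drugs are used, at no more than the failed dose.

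The three powered secondary effectiveness endpoints take over the primary definition with one change each. The HSP substudy uses the same endpoint definitions, descriptively.

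**The concern.** The itemised list is what a programmer would turn into endpoint code, and the SAP carries the unlimited criterion. Coded as written, a subject whose Class I or III dose rose above the previously failed dose at any time in days 1 to 90 would be a failure, with the Kaplan-Meier event dated inside blanking, even if rhythm was normal and the drug had been stopped by day 91. Protocol 3.1 says that subject is not a failure.

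The literal rule can be programmed from data the trial collects. Protocol 6.1 records maximum ineffective dosages at baseline, and Protocol 6.2.2 records AAD dose with start and stop dates before and after the procedure.

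Timing adds to the case for acting early. The study is single-arm and unblinded. If the conflict is noticed only after data are seen, resolving it would remove failures in the sponsor's favour. Resolved beforehand, it is a clerical correction.

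**Working it through.** No stated figure is in dispute, so the main check is a comparison of texts.

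**Step 1. Sort the nine failure criteria by whether they can apply before day 91.**

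| Criterion | Can it count before day 91? |
|---|---|
| No acute procedural success at last TactiFlex SE procedure | Yes |
| Documented recurrence | No, limited to after blanking |
| Repeat AF procedure more than 80 days after the first | Yes, days 81 to 90 |
| Second repeat AF ablation by day 80 | Yes |
| New Class I/III drug | No, limited to after blanking |
| **Dose above the previously failed dose** | **No limit stated** |
| Cardioversion for AF | No, limited to after blanking |
| Arrhythmia throughout a 12-lead ECG | No, limited to after blanking |
| Left atrial ablation with another catheter | Yes, no limit stated |

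Leaving out the disputed row, four criteria are limited to the time after blanking and four are not. Silence in this list can therefore mean that an event counts during blanking, and the list alone does not supply the missing limit.

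**Step 2. Compare with the rest of the text.** Protocol 3.1 and 6.2.2 contradict the literal reading directly. The rationale sentence in both documents names higher doses and places them after blanking. Section 6.5 is weaker support: it permits drug adjustment, but its statement about not being a failure covers only early arrhythmia recurrence. The narrative sentence is weaker too, because it deals with use after day 90 and does not expressly exempt earlier use.

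**Step 3. Direction.** The literal reading only adds failures, so it can lower the measured success rate but cannot raise it.

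**Step 4. Size, as an illustration only.** Inputs from the Protocol: 305 enrolled in the main study (5.6) and a performance goal of 50% (4.1.2). Assumed: true success rate p, the fraction f of otherwise successful subjects reclassified, one-sided alpha of 0.025, no attrition, and a simple binomial in place of Kaplan-Meier. The effectiveness population and sample-size inputs are redacted.

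- One subject: 100/305 = 0.33 points.
- Fall in the rate: 100 × p × f. At p = 0.60, f = 1%, 2%, 5% and 10% give 0.6, 1.2, 3.0 and 6.0 points.
- Success rule: the smallest r with P(X ≥ r | 305, 0.50) ≤ 0.025 is 171 (actual alpha 0.0195).
- Power: P(X ≥ 171 | 305, p(1 − f)).

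| p | f = 0 | 1% | 2% | 5% | 10% |
|---|---|---|---|---|---|
| 0.55 | 0.376 | 0.306 | 0.242 | 0.101 | 0.013 |
| 0.60 | 0.927 | 0.893 | 0.848 | 0.652 | 0.253 |
| 0.65 | 0.999 | 0.999 | 0.997 | 0.982 | 0.822 |
| 0.70 | 1.000 | 1.000 | 1.000 | 1.000 | 0.995 |

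At one-sided 0.05 the rule is 168 of 305, and the p = 0.60 row becomes 0.964, 0.944, 0.915, 0.769 and 0.374. The table shows sensitivity to f. It does not predict f.

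**The case against.** The strongest reply is that nobody reading the plan as a whole would score these subjects as failures. Protocol 3.1 says outright that they are not, 6.2.2 starts the rule at day 91, and the rationale places higher doses after blanking. Against all of that stands one line that also contains a misprint. This largely stands, and it is why the point is an inconsistency and not a wrong endpoint.

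A reader might infer that the SAP has nothing to correct the line. That goes too far. SAP 1.4.1.2 contains the post-blanking narrative before the list and the rationale sentence after it. What the visible SAP lacks is a counterpart of Protocol 3.1, 6.2.2 or 6.5. A sentence of justification is a weaker instruction than an itemised criterion.

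A reader might also infer that the endpoint allows no failures at all during blanking, so that any such failure is an error. The documents do not say this: Step 1 shows four other criteria that can be met before day 91.

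Finally, a reader might put a number on the effect, for example 2% to 5% of 305, or 6 to 15 subjects. Nothing in the documents supports that frequency. Protocol 6.2.2 recommends continuing current drugs after ablation and withdrawing them at 4 to 6 weeks unless contraindicated, so escalation is not the planned course. Such a count would also be a ceiling, since subjects who fail for another reason do not change status, and 305 counts consented subjects, not the redacted analysis population.

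**Conclusion.** The point holds as an internal inconsistency in the operative failure list, present in both documents. The higher-dose criterion has no post-blanking limit and, applied literally, contradicts Protocol 3.1 and 6.2.2 and the stated rationale. The documents do not establish that blanking-period adjustments will be scored as failures, because the surrounding text points the other way.

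The size is unknown. On 305 subjects each reclassification is worth 0.33 points, and the effect on power would be material only if the true rate were not far above the 50% goal and reclassification were not rare. Both are assumptions. The bias is conservative and could not produce a false success.

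The inconsistency passes to all three secondary effectiveness endpoints. In the AAD-free endpoint any Class I/III use after blanking is already a failure, so there the inherited criterion could add only blanking-period events.

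Confidence is high that the words are missing. It is lower on the consequence, because most of the SAP's primary effectiveness analysis text is redacted and may settle how events are timed.

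**What to change.** Reconcile the higher-dose criterion with Protocol 3.1, 4.1.2.1 and 6.2.2 by giving it the same post-blanking limit as the new-drug criterion above it, in both Protocol 4.1.2 and SAP 1.4.1.2. Correct the abbreviation from ADD to AAD in both places. The secondary endpoints and the HSP substudy then follow by reference. The Protocol's Appendix X summary does not repeat the list and needs no edit.

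The cost is a few words in each document, ideally before any outcome data are reviewed. The change affects endpoint classification only. It alters no treatment, sample size or stated figure.
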